clinical trial with a 2-arm parallel-group design to assess the efficacy of custom-fitted compression hosiery vs off-the-rack compression hosiery.

The custom stockings take 2 weeks to manufacture. In order to maintain the blind, stockings will be procured by the UT CV Surgery purchasing personnel and distributed to the subjects in unmarked packaging within three weeks of randomization. Neither the prescribing physician nor the patient will know the treatment assignment.

Screened patients meeting the eligibility criteria will have a below-knee laser measurement scan, and will be randomized into one of the two study groups.

At the screening visit, patients will be evaluated for trial eligibility and the study will be explained. For eligible patients who wish to participate, informed consent will be obtained and the patient will receive history and physical exam and will complete baseline HRQoL and pain scale surveys. Volumetric scans will be performed and the data will be stored. Patients will be randomized by a study coordinator, and will be instructed to expect stockings in the mail within 3 weeks.

After stockings are dispensed, patient should call the office to inform the study nurse or coordinator of the day they are beginning therapy, and biweekly log will be kept as a measure of compliance.

Patients in the study should also complete the Brief Pain Inventory (BPI) before randomization (at baseline following enrollment), by phone during week six, and at clinical follow-up after completing 90 days of compression therapy. Additionally, patients will be assessed on their satisfaction at week six and at 90-day clinical follow-up. This

will be done using the 5-point satisfaction scale with 1 being “very dissatisfied” to 5 being “very satisfied”. The SF-12 HRQoL instrument will also be completed at enrollment, at six weeks and at 90-day follow-up. This will conclude the 90-day treatment period. Patients will be re-contacted at six months post-treatment to determine whether they are still using their stockings (or have replaced them) or have progressed to invasive treatment. After the six-month assessment, the study will be concluded and enrollment will be terminated.

Study Conduct

1. Screening

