The PI and research staff will assess patients as possible candidates for enrollment based on the inclusion criteria described previously. A member of the research team - the PI, a Co-investigator, research coordinator, or research nurse will obtain the consent from interested patients who met the preliminary inclusion criteria. The consent process will take place during the clinic visit. Patients will be given adequate time and education about their condition to ask questions about the protocol and research study. Those who wish to participate will be informed they are responsible for the cost of the hosiery as it may not be covered by insurance (most plans do not cover stockings even though they are required prior to preauthorization for ablation therapy). Patients would be responsible for this cost whether or not they are enrolled in the trial – no additional cost to the patient will result from trial participation. The preoperative baseline pain level, using BPI and HRQoL will be recorded at this time. A copy of the signed informed consent shall be provided to the patient, a copy will be

placed in the patient's hospital chart, and a copy will be kept by the research team. Medical/surgical history, vital signs measurements, and standard clinical testing will also be performed as per the usual practice for assessment and management of CEAP class 2-5 venous disease.

2. Quality of life assessment - Brief Pain Inventory

The impact of pain on patient's quality of life will be assessed through a brief pain inventory (BPI) that should be done at enrollment, at the six week point during compression therapy and at the final clinic visit after 90 days of treatment. The BPI will be presented as an easy to comprehend questionnaire for the patients to quantify and communicate their pain experience and how it is affecting their life. It is designed such that patients with 6th-grade education should be able to complete the questionnaire on their own. Question and answers will be provided in a check-box format. The BPI that will be used on this study will be the short version. Patients with difficulty reading or who are physically unable to complete the questionnaire will be assisted by the research team based on their verbal responses to the BPI questions.

3. Enrollment

After screening for eligibility, if all inclusion/exclusion criteria are met and the patient has consented; the patient will be enrolled in the trial.

4. Randomization and Allocation Concealment

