
Randomization and allocation concealment will be performed by study personnel using a restricted-access randomization file. The sequence will be generated by a UT

statistician in a random permuted block design and copied to a secure drive accessible only to unblinded study personnel. At enrollment patients will be assigned a study ID number. The laser scan data will be identified by this study number and noted in the CRF. Depending on the group assignment, either an order for a custom pair of stockings will be generated and tagged to the scan data – which will then be transmitted to the manufacturer – or the appropriate pair of Sigvaris stockings will be procured. After two weeks, the stockings as allocated by randomization will be packed in unbranded packaging and mailed to the research subject by trackable means (UPS, FedEx, US Postal Service, etc.). The clinical personnel who assess the patients will not handle the hosiery and will not see it on the patient. The patient will not know whether the stockings are custom or off-the-rack, so the double masking will be maintained.

5. Baseline assessment

History, physical exam and review of symptoms will be conducted at enrollment and captured to an electronic case report form that will be implemented at UT in REDCap. The examining physician will draw a diagram of the involved veins for comparison with the 90-day examination. Pain assessment and HRQoL will be captured as described previously.

6. Follow-up

After the initiation visit is completed, the follow-up will be:

- i. Compression therapy per physician directive throughout 90 days with a compliance log to be kept bi weekly.*

- ii. *At 6 weeks questionnaire completion via phone.*
- iii. *At 90 days clinic follow-up and questionnaire completion*
- iv. *At six months after treatment initiation by telephone*

7. Termination of enrollment

Patient will be considered to have his/her enrollment terminated:

- i. *After completion of the six month telephone survey*
- ii. *If any medical/surgical/environmental condition develops that would affect or impair primary or secondary outcomes measurements results*
- iii. *If the study is terminated*
- iv. *If the patient dies*

8. Termination of Study

- i. *End of study period*
- ii. *Unanticipated safety problems that would make continuation unethical*
- iii. *If the trial does not look as though it can achieve its enrollment targets within two years*

XIII. ADVERSE EVENT REPORTING

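### Randomizing from a stored sequence file, with no stated one-at-a-time release and no bar on file-holders recruiting, leaves the next assignment open to being known before enrollment

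*Combined protocol and SAP*

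**What the plan says.** Section XII, Study Conduct, item 4 (Randomization and Allocation Concealment) describes the mechanism: "Randomization and allocation concealment will be performed by study personnel using a restricted-access randomization file". The sequence is produced by a UT "statistician in a random permuted block design" and is then "copied to a secure drive accessible only to unblinded study personnel". The section gives no block size and does not list which roles count as unblinded.

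The opening part of Section XII names the person who allocates: "Patients will be randomized by a study coordinator". It places this step after eligibility, consent, history and examination, baseline surveys and the volumetric scan.

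Two sections say who obtains consent. Study Conduct, item 1 (Screening) has "the PI, a Co-investigator, research coordinator, or research nurse will obtain the consent from interested patients", and the same item has the PI and research staff judge who is a candidate. Section XV.A (Informed Consent Process) lists the PI, Co-PI or co-investigators and no coordinator or nurse.

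The plan also sets out several masking measures. Stockings are bought by purchasing personnel and mailed in unbranded packaging. The clinical staff who assess patients do not handle the hosiery or see it worn. The prescribing physician and the patient are not told the assignment.

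**The concern.** Restricting access to a list keeps outsiders away from it. It does not conceal the list from the person who uses it. If the coordinator who randomizes can open a file holding the sequence, and that person or a close colleague also screens or consents, then the decision to approach, include or defer a patient can depend on what comes next.

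Three features of this trial make that more than a formality.

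- The secondary outcome section predicts in advance that patients with hard-to-fit legs will gain more from custom hosiery, and leg shape can be seen in clinic.
- One exclusion, for non-venous leg pain that could confound the results, rests on the investigator's opinion, so there is room for discretion at entry.
- The SAP relies on randomization to balance pre-intervention risk factors and names no baseline covariates for adjusting the primary comparisons.

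Selective entry by leg shape would also disturb the planned interaction analysis of calf/ankle ratio.

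A related gap concerns outcome collection. Questionnaires are completed by phone at week six, and the six-month call asks about continued use and progression to invasive treatment. The plan does not say who makes these calls, so it does not exclude someone who knows the assignments.

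**Working it through.** The documents give no figure for this point, so the check is a trace of roles and access.

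**Step 1: who can open the sequence.** Item 4 says that randomization is done from the file and that unblinded study personnel can open the drive. Section XII says that a coordinator randomizes. Read together, the randomizing coordinator is one of the people with access, or is handed assignments by someone who is. Neither place says which.

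**Step 2: is release controlled?** No section describes a central service, sealed envelopes, a locked next row or an independent holder of the list. REDCap appears only for data capture: baseline findings are "captured to an electronic case report form that will be implemented at UT in REDCap". Whether the file shows all future rows at once is not stated either way.

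**Step 3: are those with access kept out of recruitment?** Side by side:

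| Task | Who, and where stated |
|---|---|
| Opens the sequence | Unblinded study personnel, roles not listed (XII, item 4) |
| Randomizes | Study coordinator (XII, methodology) |
| Judges candidates | PI and research staff (XII, item 1) |
| Obtains consent | PI, co-investigator, research coordinator or research nurse (XII, item 1) |
| Obtains consent | PI, Co-PI or co-investigators (XV.A) |
| Makes week-six and six-month calls | Not stated |

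Under the screening section, a coordinator may both consent and randomize. Under the ethics section, a coordinator does not consent, but research staff still help to judge candidates.

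**Step 4: do the stated safeguards cover the gap?** Packaging, procurement by purchasing staff, assessors not seeing the hosiery, and masking of physician and patient all act once an assignment has been made. They concern blinding. Concealment concerns what is known before the assignment is made.

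**Step 5: how predictable could the next assignment be?** This is an illustration only. The block sizes are assumed because the plan gives none.

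- With the stored sequence open, the next assignment is known: 100%.
- With full concealment, a guess is right 50% of the time.
- In between is a person who sees past assignments only and knows a fixed block size. For blocks of 4, the chance of a correct guess at positions 1 to 4 is 1/2, 2/3, (1/3)(1) + (2/3)(1/2) = 2/3, and 1. The mean is (0.500 + 0.667 + 0.667 + 1)/4 = 70.8%. The next assignment is certain for (1/3 + 1)/4 = 33% of patients.

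| Assumed block size | Mean correct guess | Next assignment certain |
|---|---|---|
| 2 | 75.0% | 50% |
| 4 | 70.8% | 33% |
| 6 | 68.3% | 25% |
| 8 | 66.6% | 20% |

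These are rates of predictability, not of bias. They show that one-at-a-time release alone is not enough if the people who see past assignments also recruit. Separation of roles is needed as well.

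**The case against.** The strongest reply is that the plan already separates people to a fair degree. It confines the file to a defined unblinded group, which implies that other staff are blinded. It keeps physician, patient and assessors away from the product. It puts randomization after consent, baseline surveys and scan. Section XV.A would remove the overlap between consenting and randomizing altogether, and the study coordinator and the research coordinator may be different people.

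Much of this stands. The order of steps is right and should be credited, and the separation is incomplete rather than absent. But an order of steps does not conceal a list that already exists, because someone can look before deciding whom to approach. Section XV.A conflicts with the screening section, so it cannot settle who consents. The unblinded group is never named.

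Three stronger readings are tempting, and the documents do not support them.

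- A reader might infer that the whole list is on view to the coordinator who consents patients. Visibility of future rows is an inference, and the consent roles are in conflict.
- A reader might put a false-positive rate on the problem by assuming some shift between arms. The documents give no basis for choosing a shift, and selective entry and unblinded data collection would not act through the same one.
- A reader might extend the point to the compliance endpoint. Hours worn come from a diary kept by the patient, and nothing places its collection in the week-six call.

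It is also fair to say that the pain, quality-of-life and satisfaction scores are reported by patients who are meant to be masked. That limits, without removing, the influence of an unblinded caller.

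**Conclusion.** The concern holds as a weakness in the stated method: foreknowledge of the next assignment is possible and is not prevented. The documents do not show that it occurs. Its effect on the treatment comparison cannot be sized from them, in amount or in direction.

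The conclusion rests on two readings. The first is that the person who randomizes has access to the stored sequence, which follows from reading item 4 with the methodology text. The second is that no unwritten rule controls release or separates the roles. If such rules exist in practice, the remedy is to write them down. The change is worth making because a better method is available at little cost, in a trial whose staff know in advance which patients are expected to benefit.

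**What to change.** 1. Keep the sequence with the statistician, who releases one assignment at a time, or load it into REDCap so that the system does so. Remove the copy from the drive that study personnel use.
2. Release an assignment only after eligibility, consent, baseline surveys and scan are recorded. Section XII already gives this order; the change is to enforce it.
3. Send the assignment to the purchasing personnel who procure the stockings, and not to recruiting staff.
4. List the unblinded roles. State that anyone with access to the list or to assignments does not screen, consent, or make the week-six and six-month outcome calls.
5. Reconcile the screening section with Section XV.A on who obtains consent.
6. Have the statistician vary the block sizes and keep them from site staff.

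The cost is set-up time, in a system the trial already uses if REDCap is chosen, and some division of tasks among existing staff. The documents do not say how many coordinators there are, so the site should confirm that the division is workable.

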A prospective randomized-controlled trial of custom-manufactured vs. off-the-rack (OTR) compression hosiery for initial management of venous disease

Study Short Title

Custom vs OTR compression hosiery for venous disease

B. Clinical Phase

Phase IV

C. Study Population

The study will include patients aged 18 and over who have CEAP classification 2-5 venous disease and require compression as definitive therapy or in preparation for ablation therapy.

D. Study Design

Prospective double-blinded, controlled randomized clinical trial with 2-armed parallel-group sequential design

E. Sample Size

200

F. Study Duration

2 years

G. Study device and Intervention Description

Subjects will be randomized into two groups: group A will receive custom-manufactured compression hosiery (Isobar compression garment), and group B will receive off-the-rack stockings (Sigvaris).

H. Primary Objective

To assess the efficacy of custom-manufactured compression hosiery compared to off-the-rack compression hosiery for improving patient satisfaction, health-related quality of life and compliance with prescribed compression therapy

I. Secondary Objectives

- *To identify subgroups that may benefit more from custom hosiery.*
- *To determine whether improved fit affects likelihood to progress to invasive treatment.*

VI. BACKGROUND AND SIGNIFICANCE

Currently available off-the-rack compression hosiery are manufactured in eight fixed sizes (S-XLFC) that cannot be varied in size over their length to accommodate unusual anatomic patterns (eg., small ankle with large calf or vice versa) and may not achieve a comfortable fit that meets the compression goal over a uniform distribution of the limb. The custom-fitted garment is manufactured specifically for each patient based on measurements taken with a 3-dimensional volumetric laser scan of the extremity, and can be sized individually to each limb. In addition to providing data to computer assisted design-enabled manufacturing equipment, the scan data can be downloaded for analysis and may be useful for identifying patients for whom custom stockings are most beneficial and may ultimately be useful for prediction compliance and patient satisfaction. We propose to scan all trial participants prior to randomization so we can assess this in a control group as well.

VII. PRIMARY OBJECTIVES

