The target population of our study will be comprised of patients that are 18 years-old and above that present to our group at The University of Texas Medical School at Houston with venous disease requiring treatment with compression.

Inclusion/Exclusion Criteria

Patients will be *eligible for the study if:*

- 18 years-old or older, and
- Ability to comprehend and sign an informed consent and complete study questionnaires
- Patient is participating in usual work and home activities with no changes anticipated for the duration of the study
- The use of compression stocking is prescribed in accordance with the usual practice and management of venous disorders
- The patient will confirm they are willing to pay for the compression stockings.

Patients will be *excluded from the study if:*

- The patient has a known allergy to any component of the stocking (latex, etc)
- The patient has non-venous source of pain in either leg that could, in the opinion of the investigator, confound the results of the study i.e. Neuropathy, Arterial insufficiency, Diabetes
- The patient is confined to bed
- The patient has uncontrolled Congestive Heart Failure
- The patient has acute dermatitis
- The patient has weeping dermatosis
- Patients with venous ulcers will be excluded.

Protocol Deviation:

- Patient is randomized but does not receive the correct treatment assignment

Withdrawal criteria:

- Voluntary: patients who had consented and enrolled in the trial will maintain their right to withdraw at any point during the study as explained in the informed consent.
- In case of unexpected/unpredicted events, the Principal Investigator and research staff may determine that patient meets criteria for withdrawal.

X. STUDY DEVICES

The Custom stocking, (Isobar Compression Garment) is an FDA Class 1 device. The control stocking (Sigvaris) is also an FDA Class 1 device. These devices are rated at 15 mmHg compression and are comparably priced.

XI. STUDY SCHEDULE

Expected start date after IRB Approval: Eligible to begin January 2017

Expected end date for enrollment: January 2019

Length of treatment-phase enrollment for each patient: 90 days

Length of follow-up for each patient: 90 days from initiation of compression for primary endpoint; six months for assessment of likelihood to receive follow-on ablation therapy.

XII. STUDY DESIGN/METHODOLOGY

This will be a single institution, prospective, blinded, randomized, controlled

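### The masking measures stop at the parcel: nothing conceals the garment from patients who report all four primary outcomes, and no masking check is planned

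*Combined protocol and SAP*

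**What the plan says.** Section XII (Study Design/Methodology) says that neither patient nor prescribing physician will learn the allocation. Its means are that "stockings will be procured by the UT CV Surgery purchasing personnel and distributed to the subjects in unmarked packaging", within three weeks of randomization. Study Conduct item 4 (Randomization and Allocation Concealment) adds that the stockings "will be packed in unbranded packaging and mailed to the research subject by trackable means". It gives one dispatch point for both arms ("After two weeks, the stockings as allocated by randomization") and keeps the clinical assessors from handling the garment or seeing it worn. It then concludes: "The patient will not know whether the stockings are custom or off-the-rack, so the double masking will be maintained".

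Section VI adds that every participant is scanned before randomization. It also contrasts the products: the control range comes in eight standard sizes, whereas the custom garment "can be sized individually to each limb". Section X says of the two products: "These devices are rated at 15 mmHg compression and are comparably priced". Under Screening, patients are told that "they are responsible for the cost of the hosiery as it may not be covered by insurance".

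Section VII lists the primary measures: SF-12, Brief Pain Inventory, a five-point satisfaction scale, and total hours worn taken from a diary.

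**The concern.** The conclusion that masking holds does not follow from the measures listed. They work until the parcel is opened. After that the patient has the garment in hand for the treatment period, and the protocol says nothing about its appearance, markings or inserts. The protocol's own precaution for assessors makes sense only if seeing the garment might reveal the arm. The patient sees it whenever it is worn.

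The patient is also the assessor for every primary outcome, so masking the clinicians does not protect those outcomes. The main secondary comparison, progression to ablation, likewise depends on what the patient prefers. If a material share of patients infer their arm, the trial could report an expectation effect as efficacy in a double-blinded study, and it would hold no data on whether that had happened.

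**Working it through.** **1. Which cues do the described measures cover?**

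| Possible cue to the arm | Measure described | Covered? |
|---|---|---|
| Who orders the stockings | Purchasing staff; restricted allocation file (XII) | Yes |
| Parcel | Unmarked, unbranded packaging (XII) | Yes |
| Waiting time | One two-week dispatch point, delivery within three weeks (XII) | Yes, as described |
| Laser scan | Done for everyone (VI, XII) | Yes |
| Price | Products comparably priced (X) | Largely; who bills and what a receipt shows are not stated |
| Garment: brand or size marks, inserts, appearance | None | No |

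**2. Who reports the outcomes?** SF-12, Brief Pain Inventory and satisfaction are questionnaires answered by the patient. Hours worn come from the patient's own diary. That makes four of four primary outcomes.

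**3. Would unmasking be noticed?** Sections XII to XIV contain no treatment-guess question, no record of unblinding and no sensitivity analysis for it. Section XIV compares the arms directly, by mixed-effects models and a Wilcoxon test.

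**4. Illustration of scale.** The plan gives no figure for masking or bias to reproduce. Inputs:
- n = 100 per arm (XIV, sample size).
- Two-sided α = 0.05 (assumed; the plan states none).
- True effect zero.
- d = net between-arm reporting shift in SD units (assumed, as a range).

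Normal approximation for a simple two-group comparison, with √(n/2) = √50 = 7.071:

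P(significant) = Φ(7.071d − 1.96) + Φ(−7.071d − 1.96)

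- d = 0.1: Φ(−1.253) + Φ(−2.667) = 0.105 + 0.004 = 10.9%
- d = 0.2: Φ(−0.546) + Φ(−3.374) = 0.293 + 0.000 = 29.3%
- d = 0.3: Φ(0.161) + Φ(−4.081) = 0.564 + 0.000 = 56.4%

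The t-test versions are 10.8%, 29.1% and 56.0%. Both sets round to 11%, 29% and 56%, against 5% with no shift.

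The shift is an average over the whole arm. If a fraction g of patients infer their arm and their scores move by s SD, then d = g × s. For example, g = 0.5 and s = 0.2 give d = 0.1 (about 11%), while g = 0.25 and s = 0.2 give d = 0.05 (about 6%).

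**5. What would a guess question tell us?** With 100 answers per arm and a correct-guess proportion p near 0.5, the index 2p − 1 has a 95% half-width of 2 × 1.96 × √(0.25/100) = 0.196, or about ±0.20. *Don't know* answers would reduce the number contributing. That is coarse, but enough to show gross unmasking.

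**The case against.** The protocol takes masking seriously. Procurement is kept away from clinicians, the allocation file is restricted, dispatch timing is shared, everyone is scanned, prices are comparable and assessors do not see the garment. It would be wrong to say that masking rests on packaging alone. Scanning everyone protects the masking, and knowing what is being compared is not the same as knowing one's arm.

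A reader might infer several stronger things that the documents do not support:
- **That the garments carry revealing labels.** The control range has standard sizes, but no section says that either garment bears a brand or size mark.
- **That the bill reveals the arm.** Patients pay, but the billing route and the content of any receipt are not described.
- **That bias must favour custom hosiery on every outcome.** This is plausible for a product presented as possibly superior (XV.C), but nothing establishes the direction for SF-12, pain or diary hours.

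It is also fair to say that the percentages above are ordinary power figures. They would apply to any bias of that size and do not show that such a bias is likely here. The planned mixed models and Wilcoxon test would give somewhat different values.

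All of this stands. None of it supplies a measure for the garment or a check of masking.

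**Conclusion.** The point holds in a limited form. The plan asserts patient masking without describing anything that conceals the garment, all four primary outcomes are patient-reported, and no masking check is planned. As written, the trial could not tell expectation bias from benefit.

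The documents do not show that masking will fail, and they give neither the size nor the direction of any bias. The 11%, 29% and 56% figures rest on an assumed net shift of 0.1, 0.2 or 0.3 SD, no true effect, 100 analysed per arm and a two-sided 5% test. They show only that modest shifts would matter at this sample size. The existence of brand or size marks, and of a receipt naming the product, is an assumption for the investigators to confirm or rule out. The change should be made because it is cheap and supports the trial's claim to be double-blinded.

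**What to change.** In section XII (Study Design/Methodology) and Study Conduct item 4:

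1. Have the staff who repack the stockings remove or cover any brand and size marks, and take out inserts, before mailing. Keep left/right identification in the same neutral form in both arms. Any receipt should not name the product.
2. Specify that the existing start-of-therapy call is made before first wear; the text does not currently guarantee this. At that call ask which stocking the patient believes was sent: custom, off-the-rack or don't know. Report the answers by arm beside the primary outcomes. A guess at day 90 may be collected but is descriptive only: by then real fit, which is the intervention under test, can inform it.
3. Replace the assertion that masking will hold with a statement that it is attempted and will be assessed.

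Two further steps may suggest themselves but are not advised. Stripping left/right marks conflicts with a garment that may differ between limbs and could lead to swapped pairs in the custom arm. Charging one flat price could conflict with the Screening section's assurance that taking part adds no cost.

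The cost is a few minutes per parcel and one added question. The early guess does not remove bias, and the investigators may have to report partial unmasking.
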